1.2 Recruitment and selection of subjects

1.2.1 Screening/selection

Retrospective data will be collected by [name] and the VBHC data analysts at OLVG and Martini hospital.

1.2.2 Study population
 
Patients with hip osteoarthritis that were on the waiting list for THA between 1-4-2020 and 1-1-2022 and had a completed intake questionnaire will be included. The number of patients is dependent on how many patients completed the questionnaires and needs to be investigated. However, based on the waiting list at the time and the number of performed surgeries in the two hospitals, we expect to include at least 100 patients in each cohort (THA group and non-surgery group). Since we use observational data for trial emulation, no sample size calculation is needed (8).

1.2.3 Inclusion criteria
 
Inclusion criteria:
 
 - Patients on the waiting list for primary THA between 1-4-2020 up to 31-3-2022 in OLVG or Martini hospital. - Completed intake questionnaire (HOOS-PS baseline) - Indication osteoarthritis of the hip

1.2.4 Exclusion criteria
 
Exclusion criteria:
 
 - Patients that received THA on both sides within follow-up (1-4-2020 and 1-1-2022) will be excluded. - Patients with other indications than osteoarthritis of the hip were excluded.

1.2.5 Number of subjects/ sample size
 
Since we use observational data for trial emulation no sample size calculation is needed (8). The participants are already exposed to an intervention or not. Differences in the primary and secondary outcomes (PROMs) between groups will be interpreted using 95% confidence intervals and thresholds for clinical relevance which are reported below.

1.3 Data collection: variables and measurement methods
 
1.3.1 Primary outcome measure (dependent variable)
 
Primary outcome is the change score for hip function measured with the HOOS-PS at 3-months postoperative in the THA group and at least 3-months post waiting list in the control group compared to baseline. The HOOS-PS is a 5-item questionnaire that quantifies hip disability. The raw outcome is converted to a Rasch-based interval score ranging from no difficulty (0) to extreme difficulty (100) (3,4,5). The minimal clinically important difference (MCID) for the HOOS-PS is 23 points (6). We will also calculate the minimal important change in our study population, based on an anchor question.

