1.4.2 Analyses

 1. Measure if THA is effective to improve physical function in patients with osteoarthritis of the hip compared to non-surgery by means of RCT Target Trial Emulation. 2. Assessment to test the assumption that group allocation to the surgery group or non-surgery group cannot be explained by patient characteristics by means of logistic regression analysis. Secondly we test the assumption that follow-up time in days is similar between the two groups. 
1. Measure effect of THA: Two multiple regression analyses will be performed with the HOOS-PS and pain change score, respectively, as the dependent variable, and experimental condition (THA/ no-THA), age, sex, HOOS-PS score at baseline, pain score at baseline, physical therapy before baseline (yes/no) and follow-up time in days as independent variables. All regression coefficients and their 95% confidence intervals will be provided. Differences will be considered statistically significant when $p \leq 0.05$ and clinically relevant when differences exceed the MCID of 23 points for the HOOS-PS and 2 points for the NRS (6,7).
 
Descriptives on all independent variables will be presented and assessed by visual inspection of boxplots (for continuous variables) or tables (for categorical variables). These results will be provided for transparency purposes.
 
2. Test whether assumptions for target trial emulation are met. A logistic regression analysis will be performed on patients within the VBHC data set between 1-4-2020 and 1-1-2022 to check whether the group allocation cannot be explained by patient characteristics. Group being the dependent variable (THA vs. non-surgery) and age (continuous), sex (M/F), physical therapy before the hospital visit (yes/no), follow-up time in days (continuous), pain at baseline (NRS, continuous) and the HOOS-PS at baseline (continuous) will be included in the model as independent variables. Results will be considered statistically significant when $p \leq 0.05$. In case an independent variable has a statistically significant effect on the outcome, clinical relevance will be considered and discussed for the effect size on chance to be allocated to the THA or non-surgery group. Secondly, we will test the assumption that follow-up time in days is not statistically significantly different between the THA and non-surgery group. Follow-up time is defined by calculating the number of days between the date of the orthopedic visit) and the date of the follow-up questionnaire.

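### Section 1.4.2 does not name the standard-error method for the regression intervals; the default assumes equal residual variance in operated and waiting-list patients, and HC3 standard errors would remove that dependence at little cost

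*Combined protocol and SAP*

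**What the plan says.** Section 1.4.2 of the combined protocol and SAP states: "Two multiple regression analyses will be performed with the HOOS-PS and pain change score, respectively, as the dependent variable". The independent variables are treatment group and six covariates: age, sex, baseline HOOS-PS, baseline pain, prior physical therapy and follow-up time in days. On reporting, it says "All regression coefficients and their 95% confidence intervals will be provided". Significance is judged at p ≤ 0.05, and a result is "clinically relevant when differences exceed the MCID of 23 points for the HOOS-PS and 2 points for the NRS (6,7").

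Section 1.2.5 does without a sample size calculation and says instead that group differences in the PROMs "will be interpreted using 95% confidence intervals and thresholds for clinical relevance which are reported below".

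Section 1.2.2 expects a minimum of 100 patients per group, with no upper figure or ratio: "The number of patients is dependent on how many patients completed the questionnaires and needs to be investigated".

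No section names a robust, bootstrap or unequal-variance method. The boxplots and tables in 1.4.2 cover the independent variables, and 1.4.1 covers missing and extreme values. Neither is a check of residuals. No SD is given for either group.

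**The concern.** With no variance estimator named, the analyst will most likely use the default of ordinary least squares, which fits one residual variance to both groups. There is no particular reason for that to hold. One group has had surgery and is measured at 3 months postoperatively. The other is untreated and is measured at an open-ended time of 3 months or more. The score is bounded from 0 to 100.

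If residual variances and group sizes both differ, the default standard error of the THA coefficient is wrong. It is too small when the smaller group is the more variable, and too large when the larger group is. Nothing planned would reveal this. Because 1.2.5 relies on confidence intervals in place of a power calculation, their coverage is the plan's main statement about precision. The p-value rule uses the same standard error.

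**Working it through.** **Inputs from the documents.** Linear regression with treatment group and six covariates; 95% intervals; p ≤ 0.05 (taken as two-sided); at least 100 per group; thresholds of 23 (HOOS-PS) and 2 (NRS). The plan gives no SD, interval width or power, so there is no figure of its own to reproduce.

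**Assumptions.** Residual SDs of 10 to 20 HOOS-PS points, SD ratios (THA/control) of 0.5 to 2.0, and THA:control sizes from 1:1 to 6:1. Coverage depends only on the SD ratio and the group sizes, so the coverages apply to the NRS as well; the half-widths do not.

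**Formulas, ignoring covariates.**

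- Default: SE_def = √[s_p²(1/n_T + 1/n_C)], with s_p² = [(n_T−1)s_T² + (n_C−1)s_C²]/(n_T+n_C−2)
- Correct: SE_true = √[s_T²/n_T + s_C²/n_C]
- Actual coverage = 2Φ(1.96 × SE_def/SE_true) − 1

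**Worked case: 300 THA, 100 control, SDs 12 and 18.**

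- s_p² = (299×144 + 99×324)/398 = 188.8, so SE_def = √(188.8 × 0.01333) = 1.587 and the half-width is 3.11.
- SE_true = √(144/300 + 324/100) = √3.72 = 1.929, so the half-width is 3.78.
- The ratio is 0.823, so the interval is 18% too narrow. Coverage = 2Φ(1.613) − 1 = 89.3%.
- With the SDs exchanged, the half-width is 3.78 where 3.11 is correct: 22% too wide, coverage 98.3%.

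**Same formulas, other assumed values.**

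| THA:control | SDs THA/control | Default half-width | Correct half-width | Coverage |
|---|---|---|---|---|
| 100:100 | 12/18 | 4.24 | 4.24 | 95.0% |
| 150:100 | 15/18 | 4.12 | 4.27 | 94.1% |
| 150:100 | 18/15 | 4.27 | 4.12 | 95.8% |
| 200:100 | 12/18 | 3.43 | 3.90 | 91.5% |
| 200:100 | 18/12 | 3.90 | 3.43 | 97.4% |
| 300:100 | 12/18 | 3.11 | 3.78 | 89.3% |
| 300:100 | 18/12 | 3.78 | 3.11 | 98.3% |

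At 300:100 with SD ratios of 0.83 to 1.2, coverage is 92.7% to 96.8%. With ratios of 0.5 to 2.0 it is 84.9% to 99.2%. The largest half-width shift over the whole assumed range is at 600:100 with an SD ratio of 0.5: 4.00 − 2.53 = 1.47 points. The smallest among the unequal-variance, unequal-size cases is about 0.15 (150:100, SD ratio 0.83).

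**Simulation with group and six covariates** (4,000 runs per scenario, so a Monte Carlo standard error of √(0.95×0.05/4000) = 0.34 percentage points near 95%).

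- 300:100, SDs 12/18: default 90.0%, HC3 95.2%.
- 300:100, SDs 18/12: default 98.2%, HC3 95.3%.
- 100:100, SDs 12/18, follow-up time distributed differently by group (assumed means 250 and 150 days, SDs 40 and 80): default 93.3%, HC3 94.8%. Equal group sizes therefore do not fully protect the adjusted analysis.
- 300:100, SDs 15/15: half-width 3.43 default, 3.46 HC3 (3.46/3.43 = 1.01).

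HC3 coverage lay between 94.4% and 95.9% in every scenario.

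**The case against.** The strongest reply is that both triggers are assumed. The documents show neither unequal group sizes nor unequal residual variances, and the milder cases are harmless: at 150:100 with SD ratios of 0.83 to 1.2, coverage is within about one percentage point of nominal. This stands, and it rules out saying that the intervals will be wrong.

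A reader might infer that the intervals will be too narrow and overstate the evidence for THA. The documents do not support that. Baseline HOOS-PS is in the model, so what matters is the spread of the follow-up score given the covariates. Variable response to surgery could widen that spread in the THA group, bunching of good results near 0 could shrink it, and the open-ended timing in controls could widen theirs. Which group will be larger is also not stated. If the larger group is the more variable, default intervals are conservative.

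A reader might also infer that the verdict against the 23-point threshold is at risk. The clinical-relevance rule in 1.4.2 is written for the difference, not for a confidence limit, and robust standard errors leave the estimated difference unchanged. Section 1.2.5 does bring the interval into interpretation, but a shift of 0.1 to 1.5 points changes that reading only if a limit lies that close to 23 or to zero.

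Finally, the plan never states an equal-variance assumption; default standard errors are inferred from its silence. That is fair, and it is why this is an improvement to the plan and not an error in it. It does not remove the case for HC3, which needs no forecast of group sizes or variances to be approximately valid. The default does.

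**Conclusion.** The point holds as a cheap improvement of low severity. Read naturally, 1.4.2 leads to standard errors that are reliable only under a variance condition that the plan neither states nor checks. The possible error ranges from negligible to about 6 percentage points of under-coverage or 3 of over-coverage at 300:100 with SD ratios of 0.67 to 1.5 (95 − 89.3 = 5.7; 98.3 − 95 = 3.3). It is larger only under more extreme assumed ratios. All of these figures rest on assumed SDs and group sizes, and the direction cannot be known from the documents. Robust standard errors correct the interval and p-value only; they do nothing about confounding.

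**What to change.** In 1.4.2, state that the 95% confidence interval and p-value for the THA coefficient, in both the HOOS-PS and the pain regression, use heteroscedasticity-consistent (HC3) standard errors. Add that the number analysed and the residual SD will be reported for each group, so that readers can see whether the choice mattered.

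The cost is one sentence and an option in the planned software (R, SPSS). If the variances are in fact equal, intervals become about 1% wider; if the larger group is the more variable, they become narrower. Fixing the choice in advance also avoids picking a standard error after seeing the results.

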In this study we compare the effect of THA compared to non-surgery on hip disability measured with the HOOS-PS change score from baseline up to approximately 3-months by means of RCT Target Trial Emulation, which aims to mimic a traditional RCT. Function and pain as a secondary outcome are measured by means of patient reported outcome measures (PROMs) pre-operatively and post-operatively or post-waiting list. The pre-operative intake questionnaire and the 3-months postoperative questionnaire are part of standard care. The waiting list questionnaire was administered during the Covid-19 pandemic to monitor patients' health status in two Santeon Hospitals (OLVG and Martini) in all patients who were at least three months on the waiting list. Therefore our study will be performed with data of these two Santeon Hospitals. All data is available through the routinely collected data for hip osteoarthritis within the VBHC program and in addition the outcomes of the administered waiting list questionnaire. Therefore, it is not needed to obtain additional information from patients.

To test the assumption that group allocation is (pseudo)random and cannot be explained by patient characteristics or severity of pain and hip disability at baseline, a logistic regression analysis will be performed on patients within the VBHC data set between 1-4-2020 and 1-1-2022. Group being the dependent variable (THA vs. non-surgery) and age (continuous), sex (M/F), physical therapy before the hospital visit (yes/no), follow-up time in days (continuous), pain at baseline (NRS, continuous) and the HOOS-PS at baseline (continuous) will be included in the model as independent variables. Secondly, we will test the assumption that follow-up time in days is not statistically significantly different between the THA and non-surgery group. Follow-up time is defined by calculating the number of days between the date of the orthopedic visit) and the date of the follow-up questionnaire. Results will be considered statistically significant when $p \leq 0.05$. In case an independent variable has a statistically significant effect on group assignment and/or follow-up time in days is significantly different between the two groups, clinical relevance will be considered and discussed within the research team, for example the effect size on chance to be allocated to the THA or non-surgery group.

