
3.5.2. Secondary outcome measure
 
Secondary outcomes are change scores on other patient reported outcome measures (PROMs). Pain during weight bearing is measured on a numerical rating scale (NRS) ranging from 0-10. The minimal clinically important difference (MCID) for the NRS is 2 points. The anchor based questions range from 1-7 for functioning and pain. These PROMs were obtained at baseline (except the anchor based question) and at 3-months postoperatively and at least 3-months post waiting list

1.3.2 Overview of variables and measurement instruments

Variable	Measuring instrument/ Source of data	Outcome values	Measurement time
Sex	VBHC data (source is EHR*)	numeric (1 = F, 2 = M) 999 or NA is missing	Baseline
Age at time of inclusion	VBHC data (source is EHR*)	Numeric 999 or NA is missing	Baseline
Date for order THA	VBHC data (source is EHR*)	date (YYYY-MM-DD)	Baseline
Surgery date	VBHC data (source is EHR*)	date (YYYY-MM-DD) or not applicable (NA)	Date of surgery
Date completion of baseline questionnaire	VBHC data (source is EHR*)	date (YYYY-MM-DD)	Baseline
HOOS_PS_BL	HOOS_PS_PI VBHC data (source is EHR*)	HOOS-PS personal interval level score at baseline. Numeric (0-100) 999 or NA is missing	Baseline
Pain weight bearing at baseline	NRS VBHC data (source is EHR*)	numeric (0-10) 999 or NA is missing	Baseline
Patient followed physical therapy before hospital visit	VBHC data (source is EHR*)	No (0) / Yes (1) 999 or NA is missing	Baseline
Date completion of 3-months postoperative questionnaire	VBHC data (source is EHR*)	date (YYYY-MM-DD) or not applicable (NA)	3-months PO
Date completion of 3-months waiting list questionnaire	VBHC data (source is EHR*)	date (YYYY-MM-DD) or not applicable (NA)	≥ 3-months waiting list
HOOS_PS_3M_PO	HOOS_PS_PI VBHC data (source is EHR*)	HOOS-PS personal interval level score at 3-months postoperatively. Numeric (0-100) 999 or NA is missing	3-months PO
HOOS_PS_3M_WL	HOOS_PS_PI Waiting list questionnaire (source is EHR*)	HOOS-PS personal interval level score at 3-months waiting list. Numeric (0-100) 999 or NA is missing	≥ 3-months waiting list

Pain weight bearing at 3-months postoperatively	NRS VBHC data (source is EHR*)	numeric (0-10) 999 or NA is missing	3-months PO
Pain weight bearing at 3-months waiting list	NRS VBHC data (source is EHR*)	numeric (0-10) 999 or NA is missing	≥ 3-months waiting list

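### The allocation check includes follow-up days, which are fixed after allocation, and discusses effect size only when p ≤ 0.05, so a non-significant result is weak support for pseudo-random allocation

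*Combined protocol and SAP*

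**What the plan says.** Section 1.4.2, item 2, fits a logistic regression of group (THA versus non-surgery) "to check whether the group allocation cannot be explained by patient characteristics". Besides age, sex and physical therapy before the hospital visit, "follow-up time in days (continuous), pain at baseline (NRS, continuous) and the HOOS-PS at baseline (continuous) will be included in the model". Section 3.1 describes the same model.

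Both sections count follow-up days from the orthopedic visit to the follow-up questionnaire. Section 3.1 says that the waiting list questionnaire went out "in all patients who were at least three months on the waiting list". Section 3.5.2 times the outcome measures at baseline "and at 3-months postoperatively and at least 3-months post waiting list".

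The decision rule in section 1.4.2 is: "In case an independent variable has a statistically significant effect on the outcome, clinical relevance will be considered and discussed". Section 3.1 adds follow-up time to the trigger: "In case an independent variable has a statistically significant effect on group assignment and/or follow-up time in days is significantly different". Follow-up time is also compared on its own: "Secondly, we will test the assumption that follow-up time in days is not statistically significantly different between the THA and non-surgery group".

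Under item 1 of section 1.4.2, "Descriptives on all independent variables will be presented and assessed by visual inspection of boxplots" for continuous variables and tables for categorical ones; the stated purpose is transparency. The promise of coefficients with 95% confidence intervals also stands under item 1, the outcome models. Section 1.2.2 expects at least 100 patients per group and gives no power calculation.

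**The concern.** The introduction treats verification of the pseudo-random assumption as an important step and its answer as a result of the study. The closing paragraph of section 3.1 makes the causal statement conditional on that answer. The check therefore has to be informative, and two features weaken it.

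First, a variable whose end date is set by a group-specific event after allocation sits in a model of what explains allocation. The baseline coefficients are then conditional on something that group membership helps to determine.

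Second, significance is the only gate to a discussion of size. A material baseline difference that misses p ≤ 0.05 triggers nothing, and at the expected group size such a miss is common.

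**Working it through.** The documents state no power, SD or effect size for this check, so there is no figure to reproduce.

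**Inputs from the documents.** Group size n = 100 per group, an expected minimum (section 1.2.2). Significance level 0.05 per coefficient (section 1.4.2); two-sided testing is assumed, since the documents do not say.

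**Step 1. Unadjusted power.** For a baseline difference of d SD, SE = sqrt(2/n) = sqrt(2/100) = 0.141 SD.

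- d = 0.2: Φ(0.2/0.141 − 1.960) = Φ(−0.546) = 0.293. The t-test gives 0.291.
- d = 0.3: Φ(0.3/0.141 − 1.960) = Φ(0.161) = 0.564. The t-test gives 0.560.
- 80% power needs d = (1.960 + 0.842) × 0.141 = 0.40 SD.
- The 95% CI half-width is 1.960 × 0.141 = 0.28 SD, so an observed difference just below 0.28 SD would not open the discussion.
- At 200 per group the power is 52% (0.2 SD) and 85% (0.3 SD).

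**Step 2. Joint model without follow-up days.** Simulation with 10,000 data sets per scenario, 100 per group and Wald tests at 0.05. Assumptions, not in the documents: HOOS-PS/pain correlation 0.5, and the pain shifts shown. The HOOS-PS difference is 0.3 SD.

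| Pain shift (SD) | HOOS-PS flagged | HOOS-PS or pain flagged |
|---|---|---|
| 0 | 67% | 70% |
| 0.15 | 43% | 46% |
| 0.3 | 22% | 43% |

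Neither severity measure is flagged in 30% to 57% of data sets. At 200 per group, either is flagged in 94%, 75% or 70%.

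The rule also errs the other way. Under random allocation, the chance that at least one of five independent baseline tests is significant is 1 − 0.95^5 = 22.6% (simulated: 22.8%).

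**Step 3. Adding follow-up days.** Let g be the group gap in follow-up and r its within-group correlation with HOOS-PS, both assumed, with g in SD units. With no true HOOS-PS or pain imbalance, normal covariates, and follow-up linked to pain only through HOOS-PS, the HOOS-PS log-odds per SD becomes −r × g/(1 − r²) instead of 0. For g = 0.5 and r = 0.2 this is −0.10/0.96 = −0.104; the simulated mean was −0.11.

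| g | r | False HOOS-PS flags (no imbalance) | HOOS-PS flagged (0.3 SD, pain shift 0.15) |
|---|---|---|---|
| Follow-up days not in model | – | 5.0% | 43.0% |
| 0 | 0 | 5.0% | 43.0% |
| 0.5 | 0 | 5.1% | 41.1% |
| 1 | 0 | 5.0% | 36.1% |
| 0.5 | 0.1 | 5.6% | 31% |
| 0.5 | 0.2 | 9.6% | 22.2% |
| 0.5 | −0.2 | not run | 65.5% |

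The r = 0.1 row used 4,000 data sets. With no gap nothing changes. With a gap alone the loss is small to moderate. With a gap and a correlation the check can move either way.

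**The case against.** The plan is more careful than a bare significance test. The introduction says that the answer on pseudo-randomness cannot be known with certainty in advance, and the causal statement in section 3.1 is conditional. Descriptives of all independent variables will be shown, so a reader can see an imbalance whatever its p-value. The group size of 100 is a minimum, and differences of 0.4 SD or more would be found with about 80% power or better, unadjusted. A flag leads only to discussion. All of this stands and limits the consequence. It does not repair the check: the descriptives carry no decision, and the confidence intervals are promised for the outcome models, not clearly for the allocation model.

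Four stronger readings might be inferred, and the documents do not support them:

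- *That the plan equates p > 0.05 with balance.* No sentence does so. The gap is that nothing is discussed when p > 0.05.
- *That follow-up is counted from a different start in each group.* The start is the orthopedic visit in both; only the event that sets the end differs.
- *That follow-up days newly restrict the check to questionnaire completers.* Section 3.1 already defines both groups by a completed questionnaire and plans a comparison of completers with non-completers.
- *That the covariate must distort the check materially.* The large shifts in the last table need an assumed gap and an assumed correlation.

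**Conclusion.** The point holds in two parts. That follow-up days do not belong in a model of what explains allocation follows from the plan's own definitions and needs no assumption. How much harm they do is unknown: almost none without a group gap, some loss of power with a gap, and distortion in either direction if follow-up also correlates with baseline severity.

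That effect size is reached only through p ≤ 0.05 is plain from sections 3.1 and 1.4.2. At 100 per group the unadjusted detection rates of 29% (0.2 SD) and 56% (0.3 SD) rest only on the stated group size, the 0.05 level and two-sided testing. The joint-model rates also rest on the assumed correlation and pain shift.

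A reader might infer that the estimated effect of THA is itself affected. It is not: the outcome models adjust for the same baseline covariates, and the allocation check does not feed into them. What is weakened is the support for the conditional causal statement at the end of section 3.1. This should be changed, but it does not invalidate the study.

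**What to change.** 1. In sections 3.1 and 1.4.2 (item 2), remove follow-up days from the logistic allocation model and keep their separate comparison between groups. The model then holds age, sex, physical therapy, baseline pain and baseline HOOS-PS.
2. Report a standardized mean difference or odds ratio with 95% CI for every baseline covariate, whatever its p-value, and hold the research team's clinical-relevance discussion on those estimates and intervals.
3. In the closing paragraph of section 3.1, state that a non-significant check does not by itself establish pseudo-random allocation.

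The cost is a few lines of SAP text and code, slightly more reporting and a more cautious statement. No new data are needed. The check stays imprecise, with a half-width of about 0.28 SD at 100 per group, but that imprecision becomes visible to the reader.
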